Ocular screening in children and young adults at risk for increased intracranial pressure
(Pictor Plus)

Document Date: November 14, 2019

NCT03286426

Purpose of the Study

The purpose of this study is to evaluate the vision and posterior segment of eyes in children and young adults less than 22 years of age with risk, suspicion, or past medical history significant for elevated intracranial pressure (ICP). Patients will have visual acuity, confrontational visual field, and color vision tested. Assessment of the posterior segment will involve using a non-invasive (non-contact) imaging technique (i.e. a portable fundus camera in clinic and/or hospital settings).

Background & Significance

The need for non-invasive evaluation of ICP is an active area of study. The current gold standard is intraventricular or intraparenchymal catheters but these are invasive, expensive, and require sedation; and thus the need for effective non-invasive screening tools. The utility of funduscopy in identifying processes affecting ICP has long been recognized, i.e. papilledema, ocular venous engorgement, blurring of the optic disk. Studies have demonstrated that funduscopy may have a role in the qualitative assessment of increased ICP as a highly sensitive test. However, conventional bedside funduscopy does not allow for image capture and may necessitate pupillary dilation. Portable fundus cameras address these issues, allowing image capture and storage and the potential for non-mydriatic imaging, i.e. imaging without dilation of eyes. And as demonstrated in a recent study, portable fundus cameras are efficient (median exam time was 3 minutes and 24 seconds in a pediatric Emergency Department).

Additionally, ICP screening in asymptomatic patients remains limited. Patients being treated with medications for acne, specifically tetracyclines (e.g. minocycline and doxycycline), retinol, and isotretinoin, are at particular risk for increased ICP but often are not identified until they are symptomatic (i.e. headaches, visual loss, papilledema). Symptom onset has been documented from 2 weeks up to 1 year from drug initiation. The percentage of patients with subclinical asymptomatic disease is unclear. This study would allow us to describe the presence of subclinical disease in our population and the role/utility of routine non-invasive screening methods.

Design & Procedures

We plan to identify patients less than 22 years of age who present to either:

- 1) The neurosurgery service at Duke University Medical Center (Duke University Hospital, Duke South Clinics, or Duke Children's Health Center) with suspicion or history significant for increased ICP.
- 2) The dermatology service at Duke Medical Plaza Patterson Place at risk for increased ICP (i.e. those being started on or currently taking high-risk medications).
- 3) The ophthalmology service at Duke Eye Center who have risk factors consistent with either groups 1) or 2) above.

Patients may be presented with an information sheet providing a brief summary of the research study to help them decide if they want to enroll in the study. Two different information sheets will be created for the two different populations of patients from which we will be recruiting, i.e. neurosurgery

and dermatology patients. Each information sheet will focus on characteristics and risks factors of that specific patient population.

In this study, we will use an FDA-approved portable non-contact, non-mydriatic (i.e. does not require pupil dilation) fundus camera, Pictor™, to image the fundus of both eyes of study participants. There are currently 2 versions of the Pictor camera that will be used. Both versions of the Pictor camera are FDA registered Class II medical devices.

The first generation Pictor camera was registered by 510k premarket notification in 2011. Reference US FDA 510K number: K110986. The Pictor camera is developed together with Volk Optical Inc. partner Optomed and it contains Optomed technology.

The most recent generation of the Pictor camera (trademarked the Pictor Plus) was registered by 510k premarket notification in 2013. Reference US FDA 510K number: K132186. The Pictor plus is manufactured for Volk and is registered as a private label device with the FDA registered under (Smartscope Pro). Therefore its FDA 510K letter is attributable to its private label equivalent device, known as the Smartscope Pro, manufactured by Optomed Oy, from Oulo, Finland. They are exactly the same product, except for their label, thus they use Optomed Oy's K-letter for registration purposes. However, this K-letter is technically no longer applicable per the FDA because the FDA made the Ophthalmic Camera product class 510K-exempt last year.

The FDA classification of this product (Ophthalmic Camera, FDA Product Code: HKI; Regulation #: 21CFR886.1120) no longer requires a pre-market notification 510k. August 2014, the FDA determined that a number of different device classes were considered safe for use based upon a lack of reported adverse events over the years. Thus, as of August, 2014 the FDA made these device groups 510k-exempt (essentially Class I), even though they technically remain Class II. The FDA will plan to change these product groups to Class I the next time they revise the CFR (no time table set for that currently).

Patients will also have visual acuity, confrontational visual field, and color vision tested if able. No eye drops will be given for the purposes of this study. A standard visual acuity assessment, confrontational visual field, and color vision testing will take approximately 5 minutes though patients will be allowed up to 10 minutes. Expected time for imaging each eye is approximately 5 minutes with the non-contact camera.

Study participants will be followed for 1 year from the time of the initial consent. If the patient reaches 18 years of age during the study period, he/she will be reconsented with an adult consent form to continue participation in the study.

Patients enrolled into the study will be added to a customized patient list in Epic. The list will be reviewed weekly in order to keep track of upcoming appointments of enrolled study participants. At each subsequent clinic and hospital encounter, vision testing and imaging will be repeated as described above.

Images will be stored on a secure server and reviewed and evaluated by study team members. The study results will not be provided to the patient or their physician, unless any abnormalities are identified in which case appropriate referrals will be arranged.

The information that will be obtained includes the following:

- Age of study participant
- Demographic information

- Relevant past medical/surgical history (e.g. lumbar punctures, ventriculoperitoneal shunts, hydrocephalus, Idiopathic intracranial hypertension (IIH), acne or dermatology-related conditions)
- Current medications
- Clinical examination findings from medical evaluation for increased ICP (e.g. lumbar punctures, x-rays, fluoroscopy, MRI, CT)
- Clinical examination findings from their standard ophthalmic examination from both eyes (if available) including: visual acuity, pupils; anterior segment (Conjunctiva/Cornea/Anterior Chamber/Iris/Lens); and posterior segment (Vitreous/Optic nerve/Macula/ Vessels/Periphery); refraction results; clinical diagnoses.

We will evaluate:

- Images obtained from fundus photography and their interpretation
 - Visual exam findings (visual acuity, confrontational visual field, and color vision testing results)
- Selection of Subjects

Inclusion/exclusion criteria

Approximately 200 participants less than 22 years of age with risk, suspicion, or history of elevated ICP will be recruited. We plan to recruit 100 participants with history or suspicion for increased ICP from the neurosurgery service at Duke University Medical Center (i.e. Duke University Hospital, Duke South Clinic, or Duke Children’s Health Center) or the ophthalmology service at Duke Eye Center. We plan to recruit 100 participants at risk for increased ICP (i.e. those being started on or currently taking high-risk medications) from the dermatology service at Duke Medical Plaza Patterson Place or the ophthalmology service at Duke Eye Center.

-Inclusion Criteria:

Capable and willing to provide consent

Less than 22 years of age

History of or suspicion for elevated ICP or starting/currently taking high-risk medications associated with increased risk for elevated ICP

-Exclusion Criteria:

Unable or unwilling to give consent

22 years of age and older

Data Analysis & Statistical Considerations

Standard statistical methods will be used in analysis of data collected. Data will most likely be presented as the number of cases in each measured category compared to total number of cases overall, as well as the percentage of the total that each category represents.

The goal is to evaluate if patients less than 22 years old at risk for or with suspicion for or history of elevated ICP demonstrate changes in the posterior segments of their eyes detectable via portable fundus camera and what changes in visual exam are observed. Thus, we will evaluate: The posterior segments (e.g. optic nerve, retina, retinal vessels, and macula) of patients presenting with suspicion for

or history of elevated ICP and visual exam findings (visual acuity, confrontational visual field, and color vision).

Given that this is a descriptive study, we would like to recruit up to 200 patients to ensure that we enroll a wide range of clinical presentations and age ranges.

STATA, SAS, and/or JMP will be used for all statistical analysis along with the assistance of our in-house statistician as needed. Our statistician will only be given a de-identified database, which includes the following data on each subject, without any PHI:

-Age

-Ethnicity

-Relevant past medical/surgical history (e.g. LPs, VP shunts, hydrocephalus, dermatologic diagnoses, medications)

-Posterior segment findings

-Results of visual acuity, confrontational visual field, and color vision testing

-Clinical examination findings from medical evaluation for increased intracranial pressure and eye examination results

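### Drug starters imaged only at or before the first dose can stay in the denominator, which can understate subclinical disease in that group

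*Combined protocol and SAP*

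**What the plan says.** Background & Significance sets the aim for the drug-exposed group: "This study would allow us to describe the presence of subclinical disease in our population and the role/utility of routine non-invasive screening methods". Selection of Subjects then defines that group: "We plan to recruit 100 participants at risk for increased ICP (i.e. those being started on or currently taking high-risk medications". Starters and current users form one group of 100, and the split between them is not given.

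On imaging after enrolment, Design & Procedures says: "At each subsequent clinic and hospital encounter, vision testing and imaging will be repeated as described above". Encounters are found through a patient list: "The list will be reviewed weekly in order to keep track of upcoming appointments of enrolled study participants". Follow-up is bounded in time: "Study participants will be followed for 1 year from the time of the initial consent". No minimum number of images is set, and no image is tied to the start of the drug.

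Data Analysis & Statistical Considerations describes the presentation: "Data will most likely be presented as the number of cases in each measured category compared to total number of cases overall". The list of information to be collected in Design & Procedures includes current medications. The list of variables for the statistician includes medications under medical history. Neither list names a date of first dose, an image date or time on drug.

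**The concern.** An image taken at or before the first dose can record pre-existing disease, but it cannot show an effect of a drug not yet taken. The plan enrols people at that point and leaves any later image to whether they come back. A starter who does not return contributes no observation under exposure, yet on the stated presentation is one of the total against which abnormal findings are counted.

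The percentages are the study's main product, and a low one among drug starters would bear on the stated question of whether routine screening is useful. A reader could not tell whether a low figure meant little disease or little on-drug observation. With the listed variables, the analyst could not tell either.

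**Working it through.** **The plan's own figure.** The only sample-size arithmetic is 100 + 100 = 200. No expected prevalence, precision, attendance rate or starter share is stated, so p, f, s and m below are assumptions.

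**Notation.** p is the true proportion of starters with a drug-related abnormality that on-drug imaging would show. f is the share of starters with no on-drug image. s is the share of starters in the at-risk group of 100.

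**1. Dilution among starters.** If those without an on-drug image are counted as having no abnormality, and having such an image is unrelated to disease, the expected reported proportion is p x (1 - f). With p = 5%:

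- f = 10%: 5% x 0.90 = 4.5%
- f = 30%: 5% x 0.70 = 3.5%
- f = 50%: 5% x 0.50 = 2.5%

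**2. Dilution in the pooled at-risk group.** A current user's enrolment image is already on drug, so only starters lose information. If p is the same in both subgroups, the factor is (1 - s x f). With s = 50% and f = 30%: 5% x (1 - 0.15) = 4.25%. The pooled effect is smaller than the effect in starters.

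**3. How large f might be.** The documents give no visit frequency. If the number of encounters after the first dose were Poisson with mean m, f = exp(-m):

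- m = 0.5: 61%
- m = 1: 37%
- m = 2: 14%
- m = 4: 2%

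The problem could be negligible or large, and the plan has no item that would show which.

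**4. Chance of seeing any case.** As an extreme, take all 100 as starters with p = 2%. With every starter imaged on drug, the chance of at least one case is 1 - 0.98^100 = 87%. With f = 50% it is 1 - 0.98^50 = 64%.

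**5. What zero cases would mean.** The two-sided 95% exact upper limit with no cases is 1 - 0.025^(1/n):

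- n = 100: 3.6%
- n = 75: 4.8%
- n = 50: 7.1%
- n = 25: 13.7%

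If 100 starters were listed but only 50 had an on-drug image, an interval computed on 100 would claim an upper limit of 3.6% where the data support 7.1%.

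**The case against.** The strongest reply is that the miscount is inferred. The analysis section says only how data will most likely be presented. It does not define a case, and it does not rule out a separate category for participants with a baseline image only. No sentence says that a starter's first image precedes the first dose. The study is descriptive: "Given that this is a descriptive study, we would like to recruit up to 200 patients". Half the planned sample is enrolled for history or suspicion of raised pressure, and for them the point does not arise. All of this stands. It makes the point one about an unspecified denominator and a missing data item rather than a documented error.

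Restricting the denominator also has a weakness. If participants with problems return more often, the percentage among those imaged on drug could overstate disease. That stands too, and is why both denominators are needed.

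A reader might infer two stronger things. The first is that starting the follow-up clock at consent cuts starters off from the risk period in Background & Significance: "Symptom onset has been documented from 2 weeks up to 1 year from drug initiation". That interval is 365 - 14 = 351 days. Consent on the day of the first dose covers all 351; consent 14 days earlier covers 337 (96%), and 28 days earlier 323 (92%). For starters, within that range, the clock costs little. The second is that an image in the first two weeks on drug is uninformative. The cited interval is for symptom onset. The documents give no interval for subclinical disease, which may be detectable earlier, so they give no ground for discarding an early on-drug image.

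**Conclusion.** The point holds in a limited form. The plan permits a starter to have no on-drug image and still be in the total, and it lists no variable that would reveal this. The result **can** understate subclinical disease in starters, by a factor of about (1 - f), or (1 - s x f) in the pooled at-risk group. This assumes that participants without an on-drug image are counted as negative, that having such an image is unrelated to disease and, for the pooled factor, that prevalence is equal in starters and current users. The range from 5% down to 4.5%, 3.5% or 2.5% is illustrative only.

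A reader might go further and infer that the percentage will be too low. The documents do not support that: they give no attendance rate, starter share or prevalence, and attendance related to disease would alter the size of the bias. The point calls for an inexpensive change to data collection and reporting, not a redesign.

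**What to change.** **Data.** Add the date of first dose and the date of each image to the information collected under Design & Procedures, and make them available for analysis. For the statistician's de-identified file, time on drug at each image is enough.

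**Reporting**, under Data Analysis & Statistical Considerations:

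- Report starters separately from current users.
- For starters, give the percentage abnormal over those with at least one readable image after the first dose, with an exact confidence interval.
- Show it beside the percentage over all starters enrolled.
- Give the number with a baseline image only, and the distribution of time on drug at imaging. The latter also shows where a single early image may have missed later onset.

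Do not exclude on-drug images taken before two weeks. Starters need no extension of follow-up for this purpose.

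**Cost.** One extra clinical item (first-dose date) and retention of image dates; a smaller denominator with a wider interval; and possible selection towards participants who return because of problems, which showing both denominators makes visible. The change creates no image for someone who never returns. It only stops that person's pre-exposure image from being read as evidence of no drug effect.

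### The only presentation described pools two separately recruited groups of 100, and no by-group percentage is planned, so the at-risk medication group could go without one

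*Combined protocol and SAP*

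**What the plan says.** **Recruitment.** The Selection of Subjects section sets two targets that add to about 200. The first reads "We plan to recruit 100 participants with history or suspicion for increased ICP from the neurosurgery service" and allows the ophthalmology service as a second source. The other is 100 participants starting or taking high-risk medications, from dermatology or ophthalmology. Under Design & Procedures the consent materials are split in the same way: "Two different information sheets will be created for the two different populations of patients from which we will be recruiting". Ophthalmology may supply patients "who have risk factors consistent with either groups 1) or 2) above".

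**Presentation.** The section Data Analysis & Statistical Considerations says that standard methods will be used and then describes one presentation: "Data will most likely be presented as the number of cases in each measured category compared to total number of cases overall", together with each category's share of that total. No section describes a table by recruitment group, a group denominator, stratification or a comparison.

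**Aim.** Background & Significance, in a paragraph about patients on acne medications, states: "The percentage of patients with subclinical asymptomatic disease is unclear". The next sentence adds: "This study would allow us to describe the presence of subclinical disease in our population and the role/utility of routine non-invasive screening methods". The goal sentence in the analysis section names everyone: at risk, suspected, or with a history. The sentence after it, listing what will be evaluated, names only suspicion or history.

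**Dataset.** The de-identified database for the statistician lists medical and surgical history (with dermatologic diagnoses and medications among the examples), posterior-segment findings, visual results and clinical findings. Recruitment group is not a listed field.

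**The concern.** The two groups enter for different reasons. One is enrolled because raised ICP is already known or suspected; the other because a medication carries a risk of it. There is no reason given to expect the same frequency of fundus or visual findings in both. A percentage over all 200 is an average of the two group rates, weighted by the recruitment quotas, and it does not show what either rate is.

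What is at stake is mainly the at-risk group. The background calls its frequency of subclinical disease unclear and raises the utility of routine screening. A figure that includes patients with known or suspected raised ICP does not answer that. In a descriptive study the percentages are the result, so the choice of denominator is the main analysis decision.

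**Working it through.** **Inputs from the documents.** Group sizes n1 = 100 (history or suspicion) and n2 = 100 (at risk), from Selection of Subjects. The denominator is all cases, from the analysis section. The documents give no finding rates, power calculation or precision target, so the only planned figure to reproduce is the total: 100 + 100 = 200, which agrees.

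**Step 1: what a pooled count says about the at-risk group (no rates assumed).** Let T be the number with a finding among 200, everyone assessed. The at-risk count can be any integer from max(0, T − 100) to min(100, T).

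| Pooled result | Lowest at-risk count | Highest at-risk count | Possible at-risk percentage |
|---|---|---|---|
| 10/200 = 5% | 0 | 10 | 0% to 10% |
| 20/200 = 10% | 0 | 20 | 0% to 20% |
| 32/200 = 16% | 0 | 32 | 0% to 32% |
| 40/200 = 20% | 0 | 40 | 0% to 40% |

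Giving counts as well as percentages does not help, because both are taken over the overall total.

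**Step 2: how far the pooled figure can sit from the group figure (assumed rates, for illustration only).** Pooled = (n1·p1 + n2·p2)/(n1 + n2), with p1 for history or suspicion and p2 for at risk.

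- p1 = 30%, p2 = 2%: (30 + 2)/200 = 16.0%, which is 14 points above the at-risk rate.
- p1 = 10%, p2 = 5%: (10 + 5)/200 = 7.5%, which is 2.5 points above.
- p1 = 5%, p2 = 5%: (5 + 5)/200 = 5.0%, with no difference.

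In the first case the exact (Clopper-Pearson) 95% CI is 11.2% to 21.8% for 32/200 and 0.2% to 7.0% for 2/100. The pooled interval does not contain the at-risk rate.

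**Step 3: what by-group reporting costs in precision.** Exact 95% CIs at the same 5.0%:

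- 10/200: 2.4% to 9.0%, width 6.6 points.
- 5/100: 1.6% to 11.3%, width 9.7 points.

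**Step 4: can group membership be rebuilt?** Neurosurgery and dermatology recruits are placed by their service. Ophthalmology recruits may qualify by either route, so they must be placed from recorded history and medications, which are in the dataset. The remaining gap is a participant who meets both definitions, for whom no rule is given. The documents do not indicate how many there would be.

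**The case against.** The strongest reply is that the sentence is tentative. It says what is most likely, next to a general reference to standard methods, and a measured category is undefined and could be read as group crossed with finding. A reader might infer that the plan commits to a pooled-only report; the documents do not support that. This stands: a by-group table is unplanned, not excluded.

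Second, the at-risk percentage is not a stated target. The goal sentence names the combined population, which the overall figure does describe. The sample size is justified by a wide range of presentations and ages, the background refers to the study population as a whole, and the phrase about two populations concerns information sheets. This stands in part. The link to the acne-medication group is an inference, though a reasonable one given the paragraph it sits in and the separate target of 100.

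Third, nothing is lost from the data. A reader might infer that the at-risk rate becomes unrecoverable. It is unrecoverable only from the presentation described; the listed history and medications would let an analyst rebuild most of the split. What remains is that this would be done without a stated rule, possibly after results are seen.

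Fourth, the bound in Step 1 only restates that a sum does not identify its parts, and the rates in Step 2 are assumed. That is correct: the working shows what could happen, not how large the effect will be.

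**Conclusion.** The concern holds in limited form. The plan recruits two distinct groups of 100 and describes only a presentation over all cases, so the results could give one mixed percentage per finding and none for the at-risk group. With equal groups and everyone assessed, 16% overall leaves the at-risk percentage anywhere from 0% to 32%. The actual distortion depends on how far the group rates differ, which the documents do not say; if they are equal there is none.

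Importance is minor to moderate. The study is descriptive, the wording is hedged, and the split can largely be made at analysis. The documents do not support the stronger claim that the study cannot describe the at-risk group. Nor does the evaluation sentence that omits those at risk show an intention to leave them out. The goal sentence just before it includes them, and the list of what will be evaluated under Design & Procedures has no such restriction, so a drafting slip is the likelier explanation.

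**What to change.** Replace the presentation sentence in the analysis section with wording such as:

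> Counts and percentages of each posterior-segment and visual finding will be reported separately for (a) history or suspicion of elevated ICP and (b) at risk through medication, each over the number assessed in that group; any overall figure is secondary.

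The number assessed is the right denominator because visual tests are not guaranteed for everyone: "Patients will also have visual acuity, confrontational visual field, and color vision tested if able".

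Then:

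- add a recruitment-group field to the de-identified dataset, with a rule, fixed before analysis, for participants who meet both definitions;
- extend the sentence listing what will be evaluated so that it covers the at-risk group named in the goal sentence.

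The cost is a few sentences and one dataset field, with no extra patients or visits. The downside is the loss of precision in Step 3. It grows if some participants cannot be assessed: if 80 of 100 were assessable (an assumption), 4/80 = 5.0% would have an exact 95% CI of 1.4% to 12.3%.
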